Once a research coordinator is assigned, the registration information will be registered in ONCORE, which is a secure software that is password protected that is used by the CTO.

D. Eligible patients will be registered per the CTO standard procedure.

VI. Treatment Plan

A. Radiation therapy

i. **IGRT IS MANDATORY FOR THIS STUDY.**

B. Dose Specifications

i. **Pre-operative IGRT (3D-CRT or IMRT)**

1. Either 3D conformal radiotherapy or intensity modulated radiation therapy (IMRT) may be utilized as long as the dose volume histogram (DVH) constraints for critical normal structures meet the criteria defined in Section 6.4.
2. A prescription dose of 35 Gy in 5 fractions given every other day with at least 48 hours in between each fraction will be prescribed to cover 95% of the PTV.

C. Treatment Schedule:

i. Treatments will have a minimum of a 48 hour inter-fraction interval. Treatments will be completed over 20 days maximum.

ii. Patients will be treated at Froedtert Hospital or at St. Joseph's Hospital.

D. Technical Factors:

i. Megavoltage photon beams produced by linear accelerators, betatrons or microtrons with energies of ≥ 4 MV are permitted. Preoperative IGRT (3D-CRT or IMRT)

Image Guidance Devices

Image guidance may be achieved using any one or more of the following techniques:

1. Linear-accelerator mounted kV and MV conebeam CT images
2. Linear-accelerator mounted MV CT images (e.g., Tomotherapy)

Image Guidance Procedures

The institution's procedure to register treatment day imaging dataset with the reference dataset should comply with the following recommendations:

1. Imaging must be done each day.
2. Region-of-Interest (ROI) or "clip box" for image registration should be set to encompass the high dose PTV and adjacent bony anatomy
3. Both manual (e.g., based on bony anatomy) and automatic (e.g., based on mutual information) types of registration can be used; the result of the image registration must be visually checked for the alignment of the bony anatomy.

Management of Radiation Dose from IGRT

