Number of Events Prior to termination of accrual and evaluation of dose	>2
Evaluation	Assessment of treating physician, daily follow-ups with members of the radiation oncology department with toxicity specific management, documentation of care and progress.
Time to re-initiate Radiation	Once a grade 4 toxicity has resolved and at the discretion of treating radiation oncologist, the patient will be taken off study and treated to a lower dose per fraction. The physician will then close the study.
Action	Closure of trial

- vi. The treating radiation oncologist will hold any radiation treatments as they feel is necessary due to the acute grade 3 or higher toxicity and the timing of re-initiation will be determined by the treating radiation oncologist, but will generally be when the grade 3 or higher toxicity resolves.
- vii. Post-operative wound complications (not acute during radiation, as defined on Appendix III (Radiation dermatitis) are listed.
- viii. If there are any grade 5 post-operative wound complications (Appendix III), then accrual will be halted and the protocol will be reviewed.

I. Documentation Requirements

- i. Treatment interruptions should be avoided when possible by preventative medical measures and nutritional and psychological counseling. Treatment breaks and reasons need to be clearly documented.

J. Compliance Criteria

- i. Section 6 describes appropriate conduct for treatment planning dosimetry. Criteria for both major and minor deviations are provided in Section 6.7.

K. Drug Therapy

- i. Chemotherapy will be delivered prior to radiation at the discretion of the medical oncologists. Prior to radiation, patients will have a repeat MRI scan. Chemotherapeutic regimens will be determined at the discretion of the medical oncologist.

- ii. There are no concomitant medications excluded for this patient population, with exception to chemotherapy. No chemotherapy will be delivered during this course of radiation therapy.

L. Surgery

- i. Patients will have surgical resection 4 to 8 weeks after completion of radiation therapy. Prior to surgery patients will have repeat MRI scan with DCE and DWI sequences. (this is standard practice at our institution and would be done for patients not on protocol).

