 - i. Greater than 2 patients who have any grade 4 or higher toxicity during radiation. If a patient has a grade 4 or higher toxicity, then they will be taken off the study, administered a lower dose per fraction per the treating physician, and the study will be closed. We do expect grade 3 skin toxicity (moist desquamation in areas other than skin folds), as many patients have tumors that extend to the surface of the skin and thus will need to be bloused to get the appropriate dose to these areas. Thus, moist desquamation often occurs.
 - ii. ≥60% of patients with post-operative wound complications.
 - iii. As mentioned above, patients may also withdraw at any point if they wish to not be on study.
- C. The research coordinator and PI will be notified of the withdrawal of a patient and the appropriate documentation will be made.
 - i. The IRB will be notified at the time of withdrawal.
- D. Subjects will not be replaced.
- E. Follow up and data collection for withdrawn subjects will terminate at the time of withdrawal.
- F. Dose Modification
 - i. If any grade 4 toxicity occurs, the dose will be modified based on the BED calculator above and the study will be closed.

XI. **Endpoint Assessment**

- A. Study Design:
 - i. This is a non-randomized Phase II pilot protocol to determine the feasibility, toxicity, and disease control (local control, overall and progression-free survival) using hypofractionated pre-operative radiation therapy in patients with primary localized STS.
- B. Primary Endpoint:

- i. The primary aim of this study is to assess local control. We expect local recurrence rates of <7%. Local and regional recurrence will be defined for each lesion per the treating physician(s). Local recurrence will be defined if the patient has evidence of disease on imaging (MRI or CT or PET CT) or physical exam.

C. Secondary Endpoint:

- i. The secondary objective of this study is to assess quality of life, toxicity (see iii), disease-free survival and overall survival. Disease-free survival is defined as the time from enrollment until documented disease-recurrence or death, whichever occurs first. Patients who are disease-free and alive at the time of analysis will be censored at the time of their last follow-up. Patients will be followed for disease-free survival for a minimum of 2 years.
- ii. Quality of life will be assessed via the FACT-L forms and given at the specified time points above.

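### The rules for grade 4 toxicity during radiation are not reconciled: two sources are named for the modified dose, one of them defines no dose, and follow-up after leaving the study may be lost

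*Combined protocol and SAP*

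**What the plan says.** Four passages of the protocol bear on a patient with grade 4 toxicity during radiation, and none refers to another.

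- **Section VI.H.vi.** The radiation oncologist "will hold any radiation treatments as they feel is necessary due to the acute grade 3 or higher toxicity", and the restart "will generally be when the grade 3 or higher toxicity resolves". Grade 4 falls within this wording.
- **Section VI.H.v, Table 5.** Once the grade 4 event has resolved, and at the oncologist's discretion, "the patient will be taken off study and treated to a lower dose per fraction". The study then closes.
- **Section X.B.i.** For patients with an event of at least grade 4, the rule reads: "then they will be taken off the study, administered a lower dose per fraction per the treating physician, and the study will be closed". Resolution is not mentioned.
- **Section X.F.i.** "If any grade 4 toxicity occurs, the dose will be modified based on the BED calculator above and the study will be closed". The patient's study status is not mentioned.

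Three other rules touch the same patient. Section VI.C.i limits the course: "Treatments will be completed over 20 days maximum". Section VI.G.i makes an interruption a major violation only beyond two weeks, not counting weekends and holidays. Sections X.D and X.E bar replacement and end data collection when a subject is withdrawn.

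**The concern.** A treating team facing a grade 4 event has no single instruction to follow. Section VI.H.vi read alone ends with a restart on resolution. Table 5 and X.B.i end with removal from the study at a lower dose per fraction, but only Table 5 makes that wait for resolution. For the dose itself, X.B.i points to the physician's judgement and X.F.i to a calculation. That is a patient-safety ambiguity.

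The statistical stake is follow-up. The removal wording in X.B.i stands under the heading on subject withdrawal. If leaving the study means withdrawal, the patients with the worst toxicity stop contributing data. Their 2-year recurrence status and late toxicity would be missing for a reason tied to the treatment under study.

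**Working it through.** **1. The passages side by side**

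| Passage | Waits for resolution | Source of dose | Study status |
|---|---|---|---|
| VI.H.vi | yes, generally | silent | silent |
| Table 5 | yes | lower per fraction, source not named | off study |
| X.B.i | silent | lower per fraction, treating physician | off study |
| X.F.i | silent | BED calculator | silent |

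Both passages that state a status agree. The direct disagreement is in the dose column (X.B.i against X.F.i). The remaining gap is that VI.H.vi covers grade 4 without sending the reader to Table 5.

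**2. Does the BED calculator define a dose?** It can only mean Figure 1 and Table 1 of the Introduction. Inputs from Table 1: D = 35 Gy, d = 7 Gy. Figure 1 as printed is D × d/(α/β); the standard formula is D × (1 + d/(α/β)).

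| α/β | Table 1 | As printed | Standard |
|---|---|---|---|
| 0.5 | 490.0 | 35 × 7/0.5 = 490.0 | 35 × 15 = 525.0 |
| 1 | 280.0 | 245.0 | 35 × 8 = 280.0 |
| 3 | 116.67 | 81.67 | 116.67 |
| 5 | 84.0 | 49.0 | 84.0 |
| 10 | 59.50 | 24.5 | 59.5 |

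The printed equation matches the first row only and the standard formula the other four only. No single formula gives the whole table. Even with the equation settled, X.F.i names no α/β, no target BED and no number of fractions, so no dose follows from it.

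**3. Holds against the course limits.** Assume weekday treatment. A Monday, Wednesday, Friday, Monday, Wednesday course runs from day 1 to day 10, leaving 20 − 10 = 10 days. A two-week gap in place of the usual 2- or 3-day interval adds at least 14 − 3 = 11 days, so the course takes at least 21 days. That exceeds the maximum in VI.C.i but is not beyond the two weeks of VI.G.i. VI.H.vi mentions neither limit.

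**4. How many patients?** The documents give no grade 4 rate, so a range is assumed. With all 35 treated and early closure ignored, P(at least one) = 1 − (1 − p)^35: 0.297 at p = 1%, 0.656 at 3%, 0.834 at 5% and 0.975 at 10%. Closure limits the count. If the first event closes the study (X.F.i), about one patient is affected. If more than two are needed (Table 5 and the opening of X.B.i), about three are. Either way, patients under treatment at closure may add to this.

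**5. Effect on the primary result.** Section XIII concludes equivalence with at most 1 recurrence in 35. At a true rate of 12%:

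- n = 35: 0.88^35 + 35 × 0.12 × 0.88^34 = 0.066
- n = 34: 0.88^34 + 34 × 0.12 × 0.88^33 = 0.073

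(Section XIII prints 8.97% for 35 patients. That value is obtained with 32, which is a separate matter.) Losing one patient at random costs 0.007 in type I error. In a single trial it can still decide the outcome: a true 2 of 35 is seen as 1 if the lost patient is one of the two who recur.

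**The case against.** The strongest reply is that the passages form one sequence: hold until resolution (VI.H.vi and Table 5), then off study at a lower dose per fraction (Table 5 and X.B.i), with the calculator as the physician's tool (X.F.i). Table 5 comes immediately before VI.H.vi and is specific to grade 4, so it would naturally govern. This largely stands. It has to be assembled by the reader, however, and it does not say whether the physician or the calculator decides the dose.

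A reader might infer that two patients with the same event could be handled oppositely, one continuing on study at 7 Gy per fraction and the other removed. The documents do not support that. No passage says a grade 4 patient stays on study, and the silence of VI.H.vi is not a rule.

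A reader might also want to put a size on the dose ambiguity. Any figure would need a fraction size, a matching target and a timing for the event, and the protocol gives none of them. Nor does the four-week skin recovery cited in the Introduction show how long a hold would last: it describes reactions after radiation had ended, in another study.

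It is also fair to say that the Introduction links an α/β of 10 to acute toxicity and 5 to long-term toxicity. That hints at an input, but X.F.i does not adopt it. Finally, no passage says off-study patients leave the analysis. The loss of data depends on reading removal as withdrawal under X.E.

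**Conclusion.** The point holds as an unreconciled set of rules with a contradictory source for the modified dose. It does not show that patients will receive opposing treatments. The finding that the calculator defines no dose is arithmetic and needs no assumption. The conflict between holds and the 20-day maximum assumes weekday treatment.

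The number of patients is small, about one to three plus any under treatment at closure, and the average effect on type I error of losing one at random is slight (0.066 to 0.073). That calculation assumes the loss is unrelated to recurrence. Here it would follow from toxicity and a changed dose, so the assumption may fail. The follow-up concern is conditional on off study meaning withdrawn, which the protocol leaves open. The change should be made, because it is cheap and bears on patient safety and on complete data.

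**What to change.** Reconcile Table 5 (VI.H.v), VI.H.vi, X.B.i and X.F.i so that one rule applies to grade 4 events during radiation. Which rule is for the sponsor's clinicians. Name one source for any modified dose. If it is the calculator, correct Figure 1 and Table 1 so that they agree, and state the α/β, the target and the other inputs. State how a toxicity hold relates to the 20-day maximum in VI.C.i and the two-week rule in VI.G.i.

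For the analysis, separate leaving protocol treatment from withdrawing consent, and confine X.E to the latter. For patients who leave treatment without withdrawing consent, record the delivered dose, continue recurrence and toxicity follow-up, and keep them in the primary and toxicity denominators.

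The cost is an amendment to Sections VI and X and to Figure 1 and Table 1, plus continued follow-up of a few patients. The sample size does not change.

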Pilot Study Evaluating Hypofractionated Preoperative Radiation Therapy for Soft Tissue Sarcomas of the Extremity and Chest-wall

I. SCHEMA

	Preoperative Image Guided Radiation Therapy (3D CRT or IMRT)	Surgery
Register	All patients:	All patients
	Patients with stage I to III STS of the extremity or chest wall who receive neoadjuvant, adjuvant, or no chemotherapy	Limb sparing surgery 4 to 8 weeks after completion of radiation therapy
	Radiation Dose: 35 Gy in 5 fractions (7 Gy per fraction)	

Patient Population:

Patients with localized, stage I-III histologically confirmed soft tissue sarcomas of the extremity and chest-wall primaries will be eligible for this study. Patients must be medically operable and have not had prior radiation therapy to the primary sarcoma site.

II. INTRODUCTION

There has been an evolution in management for patients with soft tissue sarcomas (STS) of the extremity since the 1970's. Historically, amputation was the mainstay of treatment. However, multimodality therapy with limb-sparing surgery and radiation with or without chemotherapy has been shown to yield equivalent control and survival for patients who underwent non-limb salvage techniques (1, 2). Thus, more conservative therapies have been employed.

The sequence of radiation therapy (RT) has also been examined in the treatment of STS of the extremity. Post-operative radiation is typically administered within 4 to 6 weeks after limb-salvage surgery; however, this may be technically challenging due to the lack of a known mass, large radiation fields, and higher radiation doses in the post-operative setting. The advantages of pre-operative radiation include, but are not limited to, lower radiation dose and field size, facilitation of surgical resection, improved tumor oxygenation and less long term toxicity. Thus, the use of pre-operative radiation therapy has been investigated and been shown to be feasible, and it can lead to excellent rates of local control and survival.

DeLaney, et al. examined the use of neoadjuvant interdigitated chemotherapy and radiation in 48 patients with ≥ 8 cm STS of the extremity. Patients received mesna, Adriamycin, Ifosfamide and Dacarbazine (MAID) followed by radiation therapy to 22 Gy at 2 Gy per fraction. This sequence was repeated once followed by limb-salvage surgery and 3 additional cycles of MAID. In this study, 5-year local control was 92% and 5-year disease-free and

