 - vii. No prior radiotherapy to primary site or adjacent site that results in overlapping radiation fields.
 - viii. If patient received neoadjuvant chemotherapy, it must be completed ≥ 21 days prior to start of radiation therapy
 - ix. MRI obtained of the affected extremity or chest-wall within 16 weeks of registration
 - x. CT chest or PET/CT acquired to assess distant disease within 16 weeks of registration
 - xi. KPS 60 or above within 16 weeks of registration
 - xii. Informed consent obtained prior to registration
 - xiii. Women of childbearing potential and male participants must practice adequate contraception.
 - xiv. Documentation of no metastatic disease within 16 weeks of registration
 - xv. Documentation of sarcoma pathology in electronic medical record
 - xvi. CBC with differential within 16 weeks of registration with adequate bone marrow functioning as follows
 - 1. Absolute neutrophil count (ANC) ≥ 1,500 cells/mm³
 - 2. Platelets ≥ 100,000 cells/mm³
 - 3. Hemoglobin ≥ 8.0 g/dl (Note: The use of transfusion or other interventions to achieve a hemoglobin of ≥ 8.0 g/dl is acceptable)
 - xvii. If a female of childbearing age and potential, serum pregnancy test is required within 72 hours prior to simulation.
- B. Exclusion Criteria
 - i. Patients who have metastatic disease
 - ii. Pregnant women
 - iii. Disease pathology other than sarcoma subtypes
 - iv. Patients with a history of metastatic disease from a primary other than sarcoma
 - v. Patients who cannot undergo MRI as part of pre-treatment or treatment planning process
 - vi. STS of other than the extremity or chest wall
 - vii. Tumor size ≥ 30 cm maximal dimension; proximal medial thigh tumors (>=20 cm)
 - viii. Prior excision or resection of tumor

V. REGISTRATION PROCEDURES

- A. Patients who are screened and eligible will have a discussion with the treating physician. There is no randomization of patients on the study
- B. If the patient is amenable to the study, then the CTO will be called for the consent process. The research coordinator for the study will consent the patient, fill out eligibility forms, and assess the registration of each patient.
- C. Currently the PI's are the contacts for registration procedures and their information is below:
 - I. [name]: [name]

II. [name]: [name]

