- ii. Surgery type will be at discretion of surgeon. Pathology will evaluate the resected specimen and calculate the percent of necrotic (non-viable) tumor in the specimen. This is standard practice at most institutions is done for patients not on protocol. Pathology slides will be sent to the Wisconsin Diagnostic Laboratories ([name]). The designated pathologist reading the slides will be [name]
- iii. The patient's tissue will be stored at the MCW tissue bank. The patients will be consented for this prior to storing tissue.

M. Other Therapy

- i. Supportive Therapy
 - 1. All supportive therapy for optimal medical care will be given during the study period at the discretion of the attending physician(s).

VII. Post-Radiation and Surgery Follow-ups and Patient Assessments (Table 4)

- A. Surgery will be scheduled 4-8 weeks after completion of hypofractionation radiation therapy. After surgery, patients will be seen by the radiation oncologists or surgeons every 4 months (+/- 2 month) for years 1 and 2 from the end of surgery. The exact assessments for these follow-up appointments are listed in Table 3. A 2-year follow-up is standard in STS and then endpoints assessed are overall and disease-free survival, as well as local control, toxicity and QOL in sarcoma studies.
- B. Patients will be evaluated by a surgeon within 2 weeks (\pm 2 weeks) after surgery for evaluation of wound healing (this is standard practice).
- C. Patients will be seen 4 months (+/- 2 month) after surgery (with physical exam) and at this time repeat imaging with a CT chest and MRI of the extremity will be obtained (this is standard practice for patients not on protocol). Treatment after failure will be at the treating team's discretion and documented.
- D. Patient will be seen subsequently 4 months (+/- 2 months) afterwards with repeat imaging with a CT chest and MRI of the extremity for years 1 and 2. Anchor time points are from the end of surgery
- E. Quality of life forms (see Appendix IV) will be filled out pre-treatment and at each follow-up visit beginning at the 4 months (+/- 2 month) from surgery visit with imaging.
- F. Toxicity at all-time points will be assessed using the CTCAE version 4.0. This is the standard toxicity scoring system used in many protocols. QOL assessments will be made using the FACT-L questionnaire (Appendix IV).

Schedule of Events

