Assessments	Within 16 weeks of Registration	Prior to start of RT	During RT	Prior to Surgery (within 4 weeks of surgery)	Surgery	Surgery Follow-up (Within 4 weeks after surgery)	At 4 months (+/- 2 months) after Surgery and every 4 months (+/- 2 months) years 1 and 2
History/physical	X						X

Karnofsky PS	X			X			X
CBC with differential	X						
MRI - tumor site	X			X			X
CT Chest or PET CT	X			X			X
Pregnancy Test (if applicable)	X*						
Toxicity Evaluation		X	X	X		X	X
MSTS, FACT-L	X			X			X
Tissue Collection for Analysis	X				X		
Blood specimen for analysis	X						

Table 4: Study Parameters

*If applicable within 72 hours prior to CT simulation.

VIII. **Tissue/Specimen Submission**

- A. We will collect pretreatment diagnostic tissue and surgical specimens (1 formalin fixed paraffin embedded (FFPE) block) from patients who undergo biopsies to determine diagnosis for this research project, which is standard of care. Biopsy tissue will be sent for outside testing for RNA sequencing. The tissue will be stored on campus. The parameters to be reviewed are histologic, cell kinetic/proliferation, angiogenesis, and molecular markers have been and are under investigation. A number of biomarkers are under investigation by the Sarcoma group. These include SPARC, TYMS, RRM1, ENT1, ERCC1, TOP1, and TOP2A. These biomarkers will be assessed on biopsy and resection specimens for patients enrolled on the study. This assessment will be done in an ancillary study.
- B. Blood specimen (10 ml EDTA) will be collected at the time of lab draw (within 16 weeks of registration) for biomarker testing. Specimens will be stored on campus and sent out for cytokine analysis.

i. Process:

1. After collection, invert tube(s) multiple times to ensure adequate mixing of EDTA.
2. Centrifuge specimen(s) within one hour of collection in a standard clinical centrifuge at ~2500 RPM for 10 minutes at 4°C (preferred). If unable to process samples at 4°C then spinning at room temperature is acceptable if done within 2 hours of draw. If the interval between specimen collection and processing is anticipated to be more than one hour, keep specimen on ice until centrifuging is performed.
3. Carefully pipette and aliquot 0.5 ml plasma into as many cryovials as are necessary for the plasma collected (5 to 8) labeled with and case numbers, collection date/time, time point collected and clearly mark specimen as "plasma". Avoid pipetting up the buffy coat layer.

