- A. The primary aim of a 2-year local recurrence rate of less than 3% will be evaluated by a one-sided equivalence test with an equivalence limit of 5% and a type I error rate of 10%. The study will conclude equivalence if the 2-year cumulative incidence of recurrence is less than 12% at the 0.10 type I error level. Power calculations are based on exact binomial probability calculations with an equivalence determined by no more than 12% local recurrence rate (within 5% of 7%), assuming a true 2-year local recurrence rate of 2.5%.
- B. If the true local recurrence rate is 12%, then with 35 patients the probability of observing a recurrence rate of 3.1% or less (≤ 1 of 35) is 8.97% (one-sided type I error = 0.0897).
- C. If the true local recurrence rate is 2.5%, then with 35 patients the probability of observing recurrence of 3.1% or less (≤ 1 out of 35) is 81.0% (Power).
- D. This is as close as we can get to a one-sided equivalence test with 10% type I error and 80% power with exact binomial calculations. The probability of falsely rejecting the null hypothesis (*hypofractionation treatment is worse than standard*) with only 0 or 1 recurrence out of 35 patients is less than 10% if the actual recurrence rate is 12% or more. There will be at least 80% power to reject this hypothesis if the true recurrence is 2.5% or less.

XIV. Considerations for Toxicity, QOL, Disease-Free Survival and Overall Survival (Secondary Endpoints)

- A. Overall survival and disease-free survival will be estimated using the product limit estimator and presented as Kaplan-Meier plots. Cumulative incidence rates will be calculated for local recurrence and adverse events. Quality of life data will be summarized for each time point, and compared using non-parametric statistical methods.
- B. Toxicity will be measured via the CTCAE v. 4.0 and the MSTS score. We will compare toxicity to the standard historical control for preoperative radiation therapy in STS (NCIC, O'Sullivan et. al) (5)
- C. Quality of Life will be measured with the FACT-L validated questionnaire.

XV. References

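### The MSTS and FACT-L baseline is not tied to the start of radiation, so in patients given neoadjuvant chemotherapy it can predate or fall during that chemotherapy

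*Combined protocol and SAP*

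**What the plan says.** Section VII.E sets the timing of the questionnaires in words: "Quality of life forms (see Appendix IV) will be filled out pre-treatment and at each follow-up visit", with the follow-up visits starting 4 months after surgery. It does not say whether pre-treatment means before chemotherapy or before radiation.

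Table 4 sets the timing by column. The MSTS and FACT-L row is marked under "Within 16 weeks of Registration", then before surgery, then at the 4-monthly visits. A separate column, "Prior to start of RT", exists, but only the toxicity evaluation is marked in it.

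On chemotherapy, the Schema admits patients "who receive neoadjuvant, adjuvant, or no chemotherapy". Section VI.K.i states: "Chemotherapy will be delivered prior to radiation at the discretion of the medical oncologists". Criterion IV.A.viii reads: "If patient received neoadjuvant chemotherapy, it must be completed ≥ 21 days prior to start of radiation therapy". That anchors the end of chemotherapy to radiation, not to registration. VI.K.i also has the MRI repeated before radiation; no repeat of the questionnaires is stated.

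On analysis, XIV.A states: "Quality of life data will be summarized for each time point, and compared using non-parametric statistical methods". It names no baseline form, no change score and no split by chemotherapy. Secondary objective 3 and XIV.B name MSTS, alongside CTCAE 4.0, as a measure of toxicity. Objective 3 makes clear that the toxicity meant is that of the hypofractionated radiation.

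**The concern.** The trial has one arm, and the institutional comparison database described in XI.D lists neither FACT-L nor MSTS among its variables. For quality of life, each patient's own earlier score is therefore the main reference point. What that score represents depends on when the form was filled in.

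FACT-L asks about the past 7 days and covers energy, nausea, hair loss, appetite and weight loss, which chemotherapy can plausibly move. A form completed before chemotherapy, one completed between cycles and one completed after recovery are different baselines. Under the current schedule all three comply and would be pooled among at most 35 patients. The later scores cannot show which part of a difference came from chemotherapy and which from radiation, and a missing pre-radiation form cannot be recovered afterwards.

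**Working it through.** The plan states no figure for this point, so there is nothing to reproduce. The check is date arithmetic on the plan's own windows.

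**Inputs**
- Form window: up to 16 weeks before registration (Table 4), 16 × 7 = 112 days. I read the heading as looking back from registration.
- Gap from end of chemotherapy to first fraction: at least 21 days, or 3 weeks (IV.A.viii).
- Registration to first fraction: no limit stated. Call it *k* weeks.
- Radiation: completed within 20 days (VI.C).
- Surgery: 4 to 8 weeks after radiation (VI.L). The pre-surgery form is due within 4 weeks of surgery (Table 4), so it falls about 0 to 8 weeks after radiation.
- Length of chemotherapy: not given. Assumed range *d* = 6 to 18 weeks.

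**Step 1. Tightest case, registration on the first day of radiation (*k* = 0).** The form may be 112 days old. Taking off the minimum gap leaves 112 − 21 = 91 days = 13 weeks. Any course of up to 13 weeks can lie wholly between form and radiation.

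**Step 2. General case.** A course of *d* weeks that ends 3 weeks before radiation starts *d* + 3 weeks before the first fraction. The form may be 16 + *k* weeks old at that fraction. The course fits if *d* + 3 ≤ 16 + *k*, that is, if *k* ≥ *d* − 13.

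| Assumed course *d* (weeks) | Starts before first fraction (weeks) | Smallest *k* at which it fits (weeks) |
|---|---|---|
| 6 | 9 | 0 |
| 9 | 12 | 0 |
| 12 | 15 | 0 |
| 13 | 16 | 0 |
| 15 | 18 | 2 |
| 18 | 21 | 5 |

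**Step 3. Registration before chemotherapy.** A form completed by registration then always predates chemotherapy, and the gap to radiation has no upper limit.

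**Step 4. Span of the first contrast.** With *k* = 0, the longest interval from baseline to the pre-surgery form is 112 + 20 + 56 = 188 days, and 112/188 = 60% of it lies before the first fraction. Counted from the first fraction, the same contrast spans at most 20 + 56 = 76 days.

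**Step 5. VII.E against Table 4.** Table 4 has a pre-surgery MSTS and FACT-L. VII.E lists only pre-treatment and the visits from 4 months after surgery. The form that comes closest to isolating radiation is therefore in the table but not in the text.

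**The case against.** The strongest reply is that the trial's treatment begins with radiation, so pre-treatment naturally means pre-radiation and the form does precede it. That is a fair reading of VII.E. It is also why one should not infer that the plan takes its baseline at some time other than before radiation. What stands is narrower: the word is undefined, and Table 4 does not hold the form near the start of radiation.

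A reader might also infer that the plan credits any change in quality of life to radiation. It does not say so. XIV.A describes summaries and a comparison of time points, with no change score and no attribution. The link to radiation is written only for MSTS. There the mechanism is less clear, because MSTS scores mainly pain, function and mobility or hand use, and the documents do not show how chemotherapy would move it. If XIV.B compares follow-up MSTS levels with the historical trial, the baseline may not enter that comparison at all.

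Other mitigating facts stand. CTCAE toxicity is evaluated before radiation. Consent must precede registration, so a study form would normally follow consent and a form 16 weeks before registration is less likely, though consent has no time limit. The Introduction describes chemotherapy as less commonly used, so the affected group may be small. Scores after surgery also reflect surgery and possibly adjuvant chemotherapy, so a better baseline cannot isolate radiation at those visits.

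Finally, other entries share the column, for example "CBC with differential within 16 weeks of registration with adequate bone marrow functioning as follows", and a reader might extend the point to out-of-date eligibility or staging results. The documents do not support putting a number on that. The distant-disease figure in the Introduction comes from a trial of large, grade 2 to 3 tumors, while this trial also admits stage I disease, and chest imaging is repeated before surgery. Requiring eligibility results dated after the last cycle could not be met at registration by a patient registered before chemotherapy.

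**Conclusion.** The point holds as a fault in the assessment schedule. The MSTS and FACT-L baseline is not anchored to radiation, and a fully compliant form can precede a whole chemotherapy course: up to 13 weeks of it in the tightest case, without limit if registration comes first. The consequence is a mixing of chemotherapy and radiation effects in the comparison of time points and in the use of MSTS as radiation toxicity, greatest in the contrast from baseline to pre-surgery.

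The size of the effect on scores cannot be given. The documents state neither the share of patients receiving neoadjuvant chemotherapy nor its length, and nothing in them fixes a direction. The finding rests on the column positions in Table 4 and on there being no limit from registration to first fraction. It concerns secondary endpoints only and leaves the local-control analysis untouched. It is still worth correcting, because the change is small and a missed baseline cannot be collected later.

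**What to change.** - **Table 4:** mark MSTS and FACT-L in the column before the start of radiation, with a note that the form follows any neoadjuvant chemotherapy, for example at the simulation visit.
- **VII.E:** define pre-treatment as that time point, and add the pre-surgery form so that text and table agree.
- **XIV:** name the pre-radiation form as the analysis baseline for both instruments, and summarize results by neoadjuvant chemotherapy use. With 35 patients this split is descriptive. State that scores after surgery also carry the effects of surgery and any adjuvant chemotherapy.

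The cost is one table cell, a few sentences and one extra questionnaire for patients who already completed one at registration. The toxicity evaluation is already scheduled before radiation, so no new assessment point is needed. If the registration form is kept as well, it would describe scores before the radiation baseline.
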